3. Coping. The Post Discharge Coping Difficulty Scale (PDCDS) is an 11-item scale used to measure the degree of difficulty in coping with stress, recovery, self-care and management of medical needs, help and emotional support needed, confidence in self-care and medical management abilities, and adjustment after hospital discharge.^{170,171} The items are measured on an 11-point rating scale with higher scores indicating greater coping difficulty. The FCGs will rate the items on a scale of 0 (“not at all”) to 10 (“extremely, completely, or a great deal”). The PDCDS is reliable whether self-administered or completed by interview. The instrument measures important, yet often overlooked, factors that contribute to poor post-acute recovery experiences, which are recognized as important factors likely to impact readmission and ED visits.¹⁷²⁻¹⁷⁴ Exploratory factor analysis indicates a single dominant factor accounting for 39% of scale variance.¹⁷⁵ Reliability in adult populations is reported from 0.81¹³⁹ to 0.87.¹⁷⁵
4. Depression. Depression will be measured with the 10-item Center for Epidemiological Studies Depression Scale (CESD-10). The CESD-10 has been used as a screening tool for depression in studies with elderly patients¹⁷⁶ as well as patients with chronic conditions.^{177,178} The correlation between this instrument and the original CESD, which had 20 items, is high.¹⁷⁸ The CESD-10 reliability statistics are comparable to those for the original CESD.¹⁷⁶ Higher scores indicate greater depressed mood. Scores of 10 or greater indicate clinically significant depression. Reliability coefficients are high (0.85-0.91).¹⁷⁹
5. Positive Aspects of Care will be measured using Tarlow et al’s Positive Aspects of Caregiving Measure.¹⁶⁶ This instrument has been used in large, diverse samples of caregivers and has shown high reliability coefficients (0.89). Examples of questions include, “Providing help to my care recipient has made me feel more useful” and “made me feel good about myself.”
6. Satisfaction with study. An open-ended question that assesses participant satisfaction with participation in the study is included in the 6 month survey. Answers to these questions will provide insight into the participant experience and allow for improvements in study execution.

Aim 3: Examine the effect of technology-enhanced TPC for FCGs on healthcare costs. The Ambulatory and Home Care Record (AHCR) will be used as our healthcare cost measure. The AHCR is designed to capture costs from a societal perspective, implying that costs from all stakeholders (FCG, care recipients, and health systems) will be collected. Developed for the Canadian health system where healthcare is primarily publicly funded,¹ the AHCR will be modified for our study to collect expenditures paid for by any type of payer (e.g., commercial, government, or other insurance; and self-pay/no insurance) instead of simply publicly-financed expenditures as in the original AHCR. Third party insurance refers to any supplemental insurance over and above the primary insurance that the patient has (see Table 2). Thus, the proposed change to the original AHCR measure is only to increase clarity regarding funders and therefore we do not anticipate any threat to the AHCR's validity. The AHCR captures self-reported utilization and cost information for care provided by all FCGs and other unpaid caregivers, paid care received at home (e.g., home health care) and outside of the home (e.g., doctor/therapy appointments), as well as medications, supplies, and equipment. Out-of-pocket costs refer to all care-related expenses not paid for by the insurance. These data will be collected monthly for 6 months following each care recipient's discharge from the index hospitalization to minimize recall bias and to account for any time lag in billing systems. The FCGs will be prompted to have all bills received during the preceding month available during the monthly AHCR data collection. Agreement between care recipients' reports on the AHCR and administrative data range from moderate ($\kappa=0.41$; 95 percent confidence interval, 0.16–0.61) for physician visits to perfect ($\kappa=1.0$) for physical therapy visits.²⁵

We will report these measures, per subject, every month to minimize the impact of patients dying in the earlier part of the intervention interval. The difference in costs of readmissions and ED visits between the intervention and control patients will provide an estimate of the costs avoided due to the proposed intervention. We anticipate that some care recipients will die before 6 months and therefore we will need to address right censoring of utilization and costs due to patients dying before the end of the study. Accordingly, we will adopt appropriate econometric methods as described in the **Analytical Plan section below** to account for the possible censoring of utilizations and costs.

The time costs refer to the FCGs' time and, if the FCG is employed, the employer time lost in the course of

Table 2: Modified Framework for Assessment of Palliative Care Costs¹		
Expenditure Category	Privately-incurred Costs	Time Costs
Third party-incurred Costs (Commercial/ Medicare/ Medicaid/ Other/ No Insurance)		
3rd Party Insurance Reimbursement (Yes/No)	Out-of-Pocket	Caregiver lost time from
• Home-based services	• Home-based services	• Labor Market
• Ambulatory appointments	• Ambulatory appointments	• Household work
• Hospitalization	• Hospitalization	• Leisure
• Emergency Department Visits	• Emergency Department Visits	
• Facility care	• Facility care	
• Medications	• Medications	Employer Time Loss
• Supplies and Equipment	• Supplies and Equipment	
	• Paid house work	
	• Travel expenses	
Total 3rd party Expenditures	Total Out-of-Pocket Expenditures	Total Time Cost

providing care to the care recipient. Time costs for the FCGs will be valued by a human capital approach.¹⁸⁰ The most recently available data on current earnings by age and sex from the Bureau of Labor Statistics (BLS) will be used to impute the market value of time withdrawn from leisure and household work. In order to value lost time from the labor market, age- and sex-based earnings from the BLS will be adjusted for employer-paid benefits, vacations days and holidays.

For those FCGs who are not employed outside the home, their time lost from household work will be imputed at the hourly earnings rate for the “personal care and service occupations” category in the BLS. Thus, the proposed valuation of the lost time will be a function of whether the time is diverted from the labor market, household work, or leisure. Dr. [REDACTED] (Co-I) will lead all aspects of this Aim.

Analytical Plan

Assessment of possible imbalances in the baseline covariates that may occur between the two groups, due to randomized intervention assignment, will be made by comparing the baseline characteristics between the two groups. Categorical variables will be compared using a Chi-square test or Fisher’s exact test; continuous variables will be compared using a two-sample t-test or the Wilcoxon rank sum test, as appropriate. All analyses will be 2-sided with an alpha level of $P<.01$ for significance to account for multiple comparisons and endpoints. The intent to treat analysis will serve as the principle analysis set for efficacy assessments.

Aims 1 and 2. Statistical analyses of Aims 1 and 2 will be performed in a similar manner. Every FCG will be evaluated using various scales and survey instruments at baseline, 2 weeks, and 8 weeks post patient discharge (Table 1). We will use a response-feature analysis as our primary approach in analyzing these repeated measures data.¹⁸¹ For each FCG, the magnitude of the scores from the respective instruments will be plotted versus time (measured in months); least squares regression will be used to estimate a participant-specific rate of increase in points per month. This slope parameter estimate will be used as the response feature for each participant and is the primary endpoint for this study. The primary analysis of this endpoint will be analyzed using a two-sample t-test or Wilcoxon rank-sum test, as appropriate. The endpoints will also be analyzed using a fixed-effects linear regression model. This model will use the estimated regression-slope response-feature as the dependent variable and have independent variables consisting of intervention (yes, no) as well as any baseline covariates such as FCGs’ age, employment status, etc. These analyses will adjust for any possible imbalances in these baseline covariates among FCGs that occur due to the randomized assignment to the intervention. This analysis approach will hold for those endpoints collected only at two time points (i.e., baseline and 8 weeks).

Aim 3. Descriptive statistics, including mean, median, and standard deviation (minimum and maximum) for the utilization measures (i.e., hospitalizations and ED visits) will be provided. Considering the count nature of the utilizations, and to also account for any potential differences between the baseline characteristics of the care recipients in the two study arms, we will use Poisson regression to model various utilization outcomes.¹⁸² We expect that the gains (decreased healthcare utilization and costs) will be sustained beyond the enrollment period. Therefore, both descriptive and multivariable-adjusted measures will be estimated for the intervention period and the subsequent months post-intervention. A limitation of this economic approach will be the memory recall of the FCGs. We will provide a worksheet similar to Table 2 for all participants to help them track services and costs.

For analyses of costs, standard descriptive statistics including mean, median, standard deviation, minimum and maximum will be provided for all cost outcomes measured individually and also for the overall cost measure. The difference in overall cost between the intervention and control group will provide an estimate of the cost impact of the TPC for FCG model of care. The difference in hospitalization and ED costs between the treatment and control arms will determine the cost avoidance potential of implementing the intervention. The difference in FCG cost, a component of the overall costs, between intervention and control groups will provide evidence on the impact of the intervention on this specific cost component. Both the descriptive and multivariable-adjusted measures will be estimated for 8 weeks and 6 months. Because the distribution of healthcare costs and length of stay (LOS) are generally skewed, both the LOS and costs will be log-transformed before any estimation; the estimated coefficients can then be interpreted as the approximate percentage changes. Alternatively, we will also explore modeling costs and LOS with a generalized linear model with gamma distribution and log link.¹⁸³ Furthermore, to account for the possibility that some of the study patients will die before the six-month follow-up; we will also apply econometric methods of censored regression.^{184,185}

Data Management

Following the data safety monitoring plan (see Protection of Human Subjects), the PI and investigative team will review the data to ensure quality, adherence to study procedures, and safety at monthly study team meetings. All participant data will be coded and stored in a secure, locked cabinet in the study coordinator's office. All data will be entered into the web-based Research Electronic Data Capture (RED-Cap) database and maintained on secure, password-protected servers, accessible only to members of the study team. The database will be exported to the statistical analysis package, SAS, to be analyzed anonymously, and standard Mayo Clinic policies and safeguards will be used to protect the confidentiality of the subject records.

Expected Outcomes

The expected outcome of this study is an effective intervention to improve FCGs' transition experiences, maintain their health and well-being, and decrease overall costs of providing TPC. This new knowledge will provide valuable information about TPC for FCG as a sustainable foundation for TPC models, and extend transitional and palliative care science to contribute to the National Institute of Nursing's strategic plan priority of gathering evidence of effective palliative care/end of life interventions to compassionately support FCGs of patients with life-limiting illness.

Potential Problems & Alternative Strategies

The primary challenges in completing this study in a timely manner are recruitment of FCG participants during their care recipients' hospital stay and completion of data collection after hospital discharge. We have identified the following strategies to overcome these potential problems.

Recruitment. [name] has more than 15 years of experience achieving enrollment goals utilizing recruitment methods similar to those we will employ for this proposed study.¹⁸⁶⁻¹⁸⁹ One specific strategy is targeting recruitment during mid-day and early evening, facilitating patient and FCG availability. We have developed strong, ongoing relationships with the Palliative Care consulting teams, who have ongoing relationships with the patients and their FCGs on their caseload. These clinically based partners will also encourage study participation.

Data collection after hospital discharge. Data collection will be completed based on FCGs' preferences using computer-assisted face-to-face interviewing, telephone interviewing, or mailed questionnaires with a stamped pre-addressed return envelope. A cover letter will accompany the questionnaires sent by mail or administered via REDCap, requesting that the FCGs complete the questionnaires on the same day they receive them, if possible. The study coordinator's phone number will be included, along with the offer to administer the questionnaires over the phone or via computer, if preferred. To minimize missing data, the study coordinator will make repeated attempts to collect the data at the respective time points.

To assure maximal completeness of post-discharge data, the study coordinator will request at least 2 phone numbers (typically home and cellphone number) for all FCGs, as well as the name and phone number of another person who may know their whereabouts. Follow-up calls to

schedule data collection will be made approximately 2 weeks and then monthly after hospital discharge at the number and time of day the FCGs suggest. Depending on the participant's preference, they may choose to be contacted by text message or email instead of receiving a phone call. The study coordinator will use a cell phone with caller identification recognizable to the participants to assure completeness of follow-up data. If at first we are unable to connect, phone calls will be made at varying times during the day. Our prior experience related to completion of data collection after hospital discharge indicated that the majority of patients and FCGs do not venture far from home soon after discharge. We will provide remuneration to all FCG participants commensurate with the time spent in the study (intervention activities for intervention group, data collection for both groups) to encourage continued engagement. If a care recipient dies during the data collection period, it may be difficult to collect subsequent data from the FCG. Providing reminder phone calls as an attention control device will augment the continued engagement of control FCGs in the study. Recall of cost components will be enhanced by monthly data collection up to six months after the care recipient's index hospitalization to account for any time lag in billing systems. The FCGs will be provided a checklist and prompted to have all bills received during the preceding month available during the monthly AHCR data collection.

Resource Sharing Plan/Data Sharing Plan

The research will be disseminated at national scientific meetings, and manuscripts will be generated from the Specific Aims. A clean de-identified dataset will be available to qualified investigators through communication with the PI after primary results manuscripts are accepted.

C. Timetable

STUDY TIME LINE	Year 1				Year 2				Year 3				Year 4				Year 5			
	Tasks	Q1	Q2	Q3	Q4	Q1	Q2	Q3												
Study start-up: regulatory & training																				
Subject accrual & data collection																				
Data Analysis																				
Cost Analysis																				
Dissemination & final report																				

D. Future Directions

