Our target population is community-dwelling adult FCGs providing care to a loved one who has a serious life-limiting condition and is new to palliative care, the care recipient will also be consented into the study. A FCG is broadly-defined as the person self-identified as the family member or unpaid friend who is the primary informal caregiver for a patient with a terminal illness. The FCG may or may not be a member of the care recipient's nuclear family. FCGs and their corresponding care recipient will be approached for study enrollment by either members of the palliative care team or the study coordinator (SC) using an IRB-approved informational brochure, including contact information for members of the study team if further discussion is requested, during the care recipients' hospital stays. Alternatively, the study coordinator may call a patient's primary caregiver to introduce the study if the caregiver and the patient meet the criteria for enrollment. Interpreters will be available for individuals who have difficulty with the English language.

FCGs

Inclusion Criteria. Any adult FCG (≥ 21 years of age) of adult patients (≥ 21 years of age) hospitalized at Mayo Clinic Hospital — Rochester, Mayo Clinic Health Systems in Mankato and/or LaCrosse who receives an in-hospital palliative care consult and lives in a Minnesota, Iowa or Wisconsin county that is designated as medically underserved or rural will be invited to participate.

Exclusion Criteria. The FCGs of patients who live in Rochester, MN, will be excluded. Rochester, MN is not considered a medically underserved or rural area.^{144,145} The FCGs of patients with left ventricular assistive devices, documented chronic pain, use of home infusion pain pumps, or documented active addictive behaviors (documentation of FCG's current substance use or treatment in care recipient medical record) will be excluded from this study because of their unique needs in caregiving are not addressed by this study.

Care Recipients

Inclusion Criteria. Any adult patient (≥ 21 years of age) hospitalized at Mayo Clinic Hospital — Rochester, Mayo Clinic Health Systems in Mankato and/or LaCrosse who receives an in-hospital palliative care consult and lives in Minnesota, Iowa or Wisconsin will be invited to participate.

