Part 2: At home technology-enhanced intervention. A minimum of weekly video visits will occur during Part 2 of the study. The first video visit by the nurse with the FCG will occur within 24-48 hours of hospital discharge. During visits the nurse will: (1) Provide ongoing education, guidance, and support to the FCG to develop self-care and caregiving skills; (2) Coordinate the implementation of the community-based aspects of the transitional care plan to address the FCG's as well as the patient's needs; (3) reaffirm and provide education and anticipatory guidance for the use of individualized FCG Readiness Plans for common care recipient symptoms such as pain, breathlessness, anxiety, etc.; (4) if requested, collaborate through active dialog with the local community resources included in the transition plan; (5) if requested, collaborate with the primary care provider/specialty providers related to goals of care; (6) coach the FCG in preparation for care recipient/provider office visits; and based on her continuing assessments; and (7) provide additional video visits/phone calls to support the FCG. Palliative and transitional care intervention objectives and activities are listed in Figure 2. Frequency type and length of contacts will be documented to quantify the dose effect of the intervention.

Video visits will be accomplished via the Zoom application using the equipment of choice by the FCG: a 3G-enabled iPad (provided by the study) or their own Smartphone or personal computer enabled with a camera for video visits. Any required training on the equipment and software will be conducted by the study coordinator in person or over the phone during Part 1 of the intervention with additional 24/7 technical support provided by the study coordinator and the IT solutions contractor (Caryl Technologies, LLC) during Part 2.

The intervention will continue for the FCGs during the 8-week period. Based on our prior experience with the FCG population, it is possible that the care recipient may be placed in a long-term nursing facility or die during the 8-week study period. In the case of the death of the care recipient, bereavement support (phone calls, video visits, and written educational materials) for the FCG will be provided for the duration of the 8-week intervention interval.

Control group: Usual care condition

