The FCGs randomized to the control group will receive a phone call by a member of the study team reminding them of the study and the next scheduled data collection date. This call will account for the nonspecific conditions of expectancy, social support, and attention considered necessary to generate placebo effects.¹⁵¹ If concerns are identified during the attention control interaction between FCGs and study personnel, the FCGs will be advised to call their primary care provider. Control group care recipients will receive consult visits by the palliative care team while hospitalized, usual hospital discharge planning, and primary and specialty care in the community after hospital discharge. Services received by the FCGs will be collated and considered for analysis as confounding factors. We do not anticipate care recipients will participate in any study activities.

Study procedures

Study Preparation and Monitoring. Following IRB approval, the study coordinators and clinician members of the research team will be educated on the purpose of this study, as well as trained in all study procedures by the investigators; training will occur at study initiation and at subsequent quarterly reviews of study procedures.

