Authentication of key biological and/or chemical resources. Findings regarding sex differences in FCG outcomes ^{9,152} have not been reported, although the majority of FCGs are female.¹⁵³ Based on the unequal sex distributions in other studies of FCGs,¹⁵⁴⁻¹⁵⁶ we anticipate the enrollment of FCG female participants will be greater than males. We have no evidence to suggest that the sex distribution of FCGs will impact our outcomes.

Variables and Their Measurements

Copies of instruments we will use are found in Appendix B, including core data elements for caregiving research suggested by the Palliative Care Research Cooperative Group.¹²⁹

Table 1 summarizes the concepts, variables and measures, and timing of data collection. Data, including sample characteristics (age, sex, race/ethnicity, marital status, education, how long the FCG has been providing care to the care recipient, any computer/Smartphone experience and availability) and questionnaires, will be collected by a study coordinator from all enrolled participants after obtaining consent (baseline) via in-person interviews prior to the care recipients' hospital discharge.

Self-reported data will be obtained by computer-assisted interviews, telephone or mailed questionnaires, based on FCGs preferences, from all FCGs at 2 weeks, at the end of the intervention period (Aims 1 and 2) and at 6 months (Aim 2). If FCGs choose to complete questionnaires independently, they will have the choice of receiving a packet by mail or a link to complete questionnaire electronically via REDCap. If any FCG would like assistance completing the questionnaires, the study coordinator will provide assistance. Given the complexity of cost data, participants will be telephoned monthly for 6 months post-hospital discharge for cost data collection needed to address Aim 3.

If the care recipient dies, we will collect Aims 1 and 2 outcomes data from the FCG approximately 2 weeks later, given that grieving family members' distress and satisfaction with care should be more stable 2 weeks after their loved one's death.^{157,158}

In order to assure the safety of participants, the intervention nurse or study social worker will follow up by phone with all participants, regardless of, who report a score of >10 on depressive symptoms on any questionnaire or if an intervention or control caregiver reports via phone, survey or email information that raises the concern for elder mistreatment or abuse about family or

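### The depression safety call starts above 10, but the plan counts a score of 10 as clinically significant, so a caregiver at exactly 10 gets no score-triggered call

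*Combined protocol and SAP*

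**What the plan says.** Two current statements in the combined protocol and SAP bear on this.

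- **Safety rule** (B. Approach, Variables and Their Measurements, after the paragraph on death of the care recipient): "the intervention nurse or study social worker will follow up by phone with all participants" meeting a condition, and the score condition is those "who report a score of >10 on depressive symptoms on any questionnaire". A second condition in the same sentence covers reports suggesting mistreatment, potentially violent conflict or self-neglect. It applies in both arms and does not depend on a score.
- **Cut-off** (Aim 2 measures, item 4, Depression): the scale is the CESD-10, higher scores are worse, and "Scores of 10 or greater indicate clinically significant depression".

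Table 1 schedules depression at baseline, 2 weeks, 8 weeks and 6 months.

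On contact outside the safety rule, Figure 2 gives nurse visits in the intervention arm for weeks 1 to 8, and Part 2 of the intervention confirms the limit: "The intervention will continue for the FCGs during the 8-week period". Control caregivers receive a reminder call from the study team. If a concern comes up during that interaction, "the FCGs will be advised to call their primary care provider". The monthly calls to 6 months are for cost data.

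**The concern.** A safety trigger would be expected to start no higher than the score the plan itself treats as clinically significant. Here it starts just above it. Staff who apply the rule literally, or who build it into an automatic alert, would pass over a caregiver at exactly 10.

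What is at stake is participant safety, not inference. Caregivers may complete questionnaires alone, by mail or REDCap link, so the score rule may be the only thing that prompts a clinician to call. If the care recipient dies, the Aim 1 and 2 outcomes are collected about 2 weeks later, so the same rule may be applied to newly bereaved caregivers.

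**Working it through.** No sample size, power or error rate is involved. The check compares the two rules as sets and then looks at when the depression score is collected.

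**1. The two rules, for a depression score s**

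- Call (safety rule): s > 10.
- Clinically significant (CESD-10 description): s ≥ 10.
- Significant but not called: s ≥ 10 and not s > 10, which leaves s = 10 only.

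| Score | Clinically significant? | Score-triggered call? |
|---|---|---|
| 9 | No | No |
| 10 | Yes | **No** |
| 11 or more | Yes | Yes |

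The disagreement is at exactly 10 whatever the scoring detail. If scores are whole numbers (assumed, since the documents give no item scoring), the lowest score that triggers a call is 11, one point above the cut-off.

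**2. Is the same scale meant?** The safety sentence names no instrument. The CESD-10 is the only depression scale described and the only measure given a cut-off of 10, so the link is an inference, but a strong one.

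**3. Could the symbol have been lost in text extraction?** The ≥ sign prints correctly in the caregiver age criterion (Sample, FCGs, Inclusion Criteria), and the cut-off is spelled out in words. Loss cannot be fully excluded, but there is no positive sign of it.

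**4. Where could other contact pick up a score of 10?** Scheduled readings: baseline + 2 weeks + 8 weeks + 6 months = 4, of which 4 − 1 = 3 follow discharge.

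| Post-discharge reading | Control: study-clinician contact scheduled? | Intervention: study-clinician contact scheduled? |
|---|---|---|
| 2 weeks | No | Yes |
| 8 weeks | No | Yes, but nurse contact is ending |
| 6 months | No | No |

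Readings without such contact are therefore 3 of 3 in the control arm and 1 of 3 in the intervention arm. The intervention figure becomes 2 of 3 if the 8-week reading is taken to fall after the last nurse visit. The control entries rest on the plan not saying that the reminder caller is a clinician. These counts describe scheduled contact, not missed cases of depression.

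**5. After the change.** With the trigger at s ≥ 10, the two rules coincide and no clinically significant score is left without a call.

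**The case against.** The strongest case on the other side has five parts.

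- **The thresholds serve different purposes.** One describes a screening instrument and the other tells staff when to telephone, so they need not match. That is true in principle, but the plan gives no reason for a stricter trigger. The call is itself only a first step: assess risk, discuss coping and resources, refer if needed.
- **The safety sentence is visibly damaged.** Words are missing just before the score condition, so this may be a slip. That is possible. If so, the sponsor can confirm it at once, and the sentence still needs correcting.
- **Other documents may hold the operative rule.** The plan points to a data safety monitoring plan, an instrument appendix and a procedure manual that are not in the public file. One of them may state ≥10. The protocol text would still disagree with itself.
- **Other safeguards exist.** After the safety rule, the plan calls for best-practice assessment of depression risk and action on any suspicion of self-harm. Read in order, these steps follow a trigger and do not replace one. Nurse visits help in the intervention arm, but the plan gives the nurse access to baseline data and does not say that she sees later scores.
- **A lower trigger has a cost.** The calls also reach control caregivers, may be made by the intervention nurse, and can cover coping. Coping and depression are Aim 2 outcomes, so this adds a little intervention-like contact in the control arm. This point stands, but it is small beside the safety purpose.

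**Conclusion.** The concern holds as written. The safety rule excludes exactly one score, 10, that the plan itself classes as clinically significant, and nothing in the available text reconciles the two.

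The effect is narrow. Its frequency cannot be computed from the documents. It does not touch the efficacy results: the Analytical Plan for Aims 1 and 2 uses a per-person slope, and no depression cut-off enters the analysis or the sample size.

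The conclusion rests on two assumptions: that the safety rule refers to the CESD-10, and that the printed > is what the plan intends. Because this is a participant-safety threshold and the correction is simple, it should be made and not left to local interpretation.

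**What to change.** In the safety paragraph of Variables and Their Measurements, change >10 to ≥10 and name the CESD-10 as the score in question. Restore the missing words in the same sentence. Keep the existing reference to any questionnaire, so that the rule covers computer-assisted interview, telephone, mail and REDCap completion alike. Make any procedure manual or database alert match.

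The cost is one symbol, a short clarification, and additional telephone calls by staff already assigned to make them. How many calls is unknown for the same reason that the number affected is unknown. Some will go to control caregivers. The plan already requires these conversations to be documented, so they can be counted by arm without new data collection. No endpoint, alpha level or sample size changes.
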